Coversheet for ClinicalTrials.gov

Title: A shortened antiepileptic drug (AED) course in surgical brain tumor patients: a randomized trial

NCT02334722

Principal Investigator: [name] MD MS

Version Date: 30 October 2019

IRB Protocol

Title: A shortened antiepileptic drug (AED) course in surgical brain tumor patients: a randomized trial

Principal Investigator: [name] MD MS

SubInvestigators: [name] MD, [name] MD

Study Coordinator: [name], BSHS, CCRC

Abstract: Seizures are one of the leading neurologic complications in brain tumor patients. This has led neurosurgeons to use antiepileptic drugs (AEDs) as prophylaxis. However, the drugs are often not withdrawn right away and patients are referred to oncologists for follow-up care. Neither specialty has particular expertise dealing with antiepileptic drugs and as a result, there has been no standardized protocol used to discontinue the drugs and many patients stay on them indefinitely. The result has been considerable practice variation in regard to the use and length of AEDs in the post-operative period². The American Academy of Neurology (AAN) guidelines recommend the discontinuation of Antiepileptic Drugs (AEDs) after the first post-operative week in patients without seizures¹. In an attempt to develop Neurosurgery clinical guidelines for AED use in post-operative brain tumor patients, we will evaluate two different courses of levetiracetam.

Patients who have had a surgical resection of a brain tumor will be randomized to levetiracetam for one week or for six weeks. The primary study endpoint will be performance on a validated neurotoxicity scoring system at 6 weeks post-op. We hypothesize that patients on a shortened AED course (1 week) will have less neurotoxicity as measured by a validated neurotoxicity scoring instrument compared to patients on 6 weeks of treatment. Secondary endpoints will include number of seizures and adverse events. We will also measure medication adherence, and mood alterations to determine if these have any correlation with AEDs.

Version Date: 30 October 2019

Background: Up to 35% of patients undergoing craniotomy for non-acute traumatic pathology experience post-operative seizures within the first week¹. A recent Cochrane database systemic review by Pulman *et al.* reviewed six randomized control trials that aimed to determine the efficacy and safety of prophylactic AED use in patients undergoing craniotomy for non-traumatic pathology. Only one trial reported a significant difference in early seizure outcomes between patients on prophylactic AEDs and control patients². The authors concluded that evidence is limited to suggest prophylactic AEDs are effective in preventing post-operative seizures. This systematic review included patients with non-traumatic pathology rather than with brain tumors alone, who may be at further increased seizure risk compared to other non-traumatic pathologies.

Prophylactic use of AEDs for patients undergoing craniotomy for brain tumors is common practice, and in a recent survey conducted by Glantz et al., 81% of practicing neurosurgeons reported that they prescribed prophylactic AEDs post operatively to patients without a history of seizures³. However, there are no clear clinical guidelines to support this practice, raising the question of whether prophylactic AEDs improve seizure incidence or subject patients to unnecessary medication side effects. Ansari et al. performed a retrospective analysis of seizure occurrence with and without post-operative AED prophylaxis over a six-year period and found no statistically significant benefit to prophylactic post-operative AEDs for intra-axial tumors⁴. Additionally, their study observed a trend (not statistically significant) of higher seizure incidence in patients receiving prophylactic AED therapy. Garbossa et al. performed a retrospective two-center cohort study of AED prophylaxis in surgically treated high-grade gliomas to assess effectiveness of perioperative AED use⁵. They reported that AED use does not provide substantial benefit. Wu et al. performed a prospective randomized clinical trial of phenytoin for perioperative seizure prophylaxis in patients with intra-axial tumors⁶. They found no benefit from AED use and increased adverse events post-operatively with AED use. Additionally, their study found a low overall incidence of post-operative seizures. Therefore, the traditional factors that are felt to increase seizure risk such as intra-axial tumors, cerebral edema, etc., have not been found to justify the routine use of AEDs in surgical brain tumor patients.

Hypothesis: We hypothesize that patients on a shortened AED course (1 week) will have less neurotoxicity as measured by a validated neurotoxicity scoring instrument compared to the patients on 6 weeks of keppra.

Primary Objective: To determine the difference in patient reported neurotoxicity associated with a shortened course (1 week) of levetiracetam compared to a longer course (6 weeks).

Secondary Objectives: To determine if seizure rates, medication adherence and mood alterations correlated with a shortened or longer course of levetiracetam.

Patient selection criteria:

Inclusion criteria -

- Adult (>18 years of age and older) patients who have or will have undergone surgical resection or biopsy of a supratentorial brain tumor and are able to consent for themselves. During the informed consent process subjects with perceived cognitive disability will be excluded from study participation.
- Able to be randomized prior to or up to 48 hours after surgery.

Exclusion criteria -

- Known history of seizure activity
- Pregnant or breastfeeding
- Renal dysfunction (CrCl<30ml/min)
- Beck's Depression Inventory (BDI) ≥14.(Subjects will have the BDI administered at baseline visit, prior to randomization. Those who score ≥14, will be excluded from the study and referred to clinical psychology. Subjects who select "2" or "3" on question 9, will be referred to clinical psychology without regard to the overall total score.)
- Allergy to levetiracetam

Research Plan:

After obtaining informed consent, subjects will be randomized into one of the following arms to receive study drug as follows:

- 1) Levetiracetam (Keppra at a daily dose of 1000mg (administered as one 500 mg tablet)PO twice daily for one (1) week.
- 2) Levetiracetam (Keppra) at a daily dose of 1000mg (administered as one 500 mg tablet)PO twice daily for six (6) weeks.

A simple randomization scheme will be used and will be generated by our statistician. All patients will be weaned off of the AED over 2 days by decreasing the dose to 500mg po every day for 2 days and then stop. The taper is to commence at day 5 for the one week group and at 2 days prior to the stop date for the 6 week group. The taper will be included on their prescription instructions and in the patient's discharge instructions to ensure proper taper of the drug. As is protocol, patients are given verbal instructions of all of their discharge medications prior to discharge along with a "teach back" method to confirm they understand how to take and stop their medications when they go home. Patients will begin study medication 48 hours post-op, regardless if they are discharged or remain hospitalized. At discharge, they will continue the medication regimen for the amount of time they were randomized.

Participants will maintain a diary that will collect seizure occurrences and daily medication intake. The RedCap database will be used to collect patient data. Participants will also complete the Beck Depression Inventory (BDI) and Neurotoxicity Scale⁷ to assess mood changes and level of cognitive functioning at baseline (preoperatively or 24-48hrs postoperatively) and at 6 weeks postoperatively. Patients with a BDI score suggestive of mild mood disturbance or depression (BDI score \geq 14) will be further evaluated by the Principal Investigator. This evaluation may include discontinuing leveteracitam, the initiation of antidepressant medications, or referral to clinical psychology. Patients will be followed until study completion and study activities will be conducted per the following Table of Events.

Activity	Baseline	Study Completion**
	(24-48 hours post-op)	6 weeks postop (+/- 4days)
Inclusion/exclusion criteria	X	
Informed consent	X	
Dispense prescription	X	
Dispense diary	X	
Collect or record diary data		X
Beck Depression Inventory (BDI)	X	X
Neurotoxicity Scale	X	X

^{**}May be completed during a routine office visit or by telephone

Data will be collected by the clinical trial coordinator and kept in an encrypted and password protected database in the coordinator's locked office. Only the investigators and study coordinator will have access to the data with identifiers. At the conclusion of the study, the data will be deidentifed and the key will be kept in a secure location in the coordinator's locked office. The key will be kept until the study is completed and the manuscript is accepted for publication.

Subjects will be assigned a unique ID number and the following data points will be captured in the RedCap database:

- Unique study ID number
- Complete past medical and surgical history
- Family history of seizures
- Tumor pathology results
- Tumor imaging findings
- Concomitant Medications
- Neurotoxicity scale scores
- BDI scores
- Seizure Diary responses

• Records of side effects or symptoms experienced

Adverse events will be collected by the study coordinator at the six week evaluation or sooner if the patient contacts their physician/study team about new symptoms/problems. These events will be documented in the RedCap database. To ensure subject safety, each adverse event will be reviewed by an independent medical monitor ([name]) to determine if it is treatment-related. After each treatment-related adverse event that is "Serious and probable" or "Serious and definite" is identified, the study statistician will use a dynamic sequential testing method to determine if the proportion of enrolled patients who have experienced these types of adverse events up to that time has statistically exceeded a maximum acceptable proportion of 10%8. This method employs a concave alpha-spending function that allows a greater chance of detecting an unacceptably high adverse event rate earlier in the study while maintaining a nominal one-sided Type I error rate of 10% over the entire sequence of tests. Using a similar sequential testing approach, the odds ratio for experiencing a treatment-related adverse event between the two arms of the study will be tested for difference from 1 .after each adverse event, at a nominal two-sided sequence-wide Type I error rate of 20%. If either the maximum acceptable adverse event rate is exceeded, or odds ratio foradverse events between the 2 study arms is found to differ from one, study enrollment will be stopped for further evaluation of patient safety.

At the completion of the study, the scores on the neurotoxicity scale will be compared between the two groups. The analysis will be performed in an intent-to-treat manner. The groups will be compared using the Mann-Whitney test for the neurotoxicity scores and Fisher's exact test for the seizure rates. Using the neurotoxicity scale, we will need 38 patients in each group to show a difference of 5.4 points in the scale with a power of 80%. The maximum score on the scale is 81^7 .

Possible discomforts or risks: Study participants may suffer from seizures related to their brain tumor or demonstrate side effects from using levetiracetam which may include:

Version Date: 30 October 2019

Sleepiness

Weakness

Infection

Dizziness

Other possible risks of levetiracetam may include:

Mood and behavior changes such as aggression, agitation, anger, anxiety, apathy,

mood swings, depression, hostility, irritability and psychotic symptoms

Hallucinations delusions and unusual behavior.

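### Allocation is allowed before surgery, in conflict with the plan's own baseline schedule and well ahead of the first dose; randomize after surgery, once baseline is complete

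*Combined protocol and SAP*

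**What the plan says.** The instructions on order and timing are spread over four places in the combined protocol and SAP.

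- **Inclusion criteria.** Surgery may still lie ahead at entry: "patients who have or will have undergone surgical resection or biopsy of a supratentorial brain tumor". Allocation may come before or after it: "Able to be randomized prior to or up to 48 hours after surgery".
- **Abstract.** Allocation follows surgery: "Patients who have had a surgical resection of a brain tumor will be randomized".
- **Exclusion criteria and Research Plan, on what must precede allocation.** "Subjects will have the BDI administered at baseline visit, prior to randomization", and "After obtaining informed consent, subjects will be randomized into one of the following arms". A BDI score of 14 or more excludes the patient.
- **Research Plan, on baseline.** The text takes the BDI and the Neurotoxicity Scale "at baseline (preoperatively or 24-48hrs postoperatively) and at 6 weeks postoperatively". It then says that study activities follow the Table of Events, whose only baseline column is headed "24-48 hours post-op". That column holds the eligibility check, consent, both scales, and the issue of the prescription and diary.

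On drug start, the Research Plan says "Patients will begin study medication 48 hours post-op". The analysis is by intent to treat, with a Mann-Whitney test on neurotoxicity scores and Fisher's exact test on seizure rates. The primary endpoint is the score six weeks after surgery. No baseline adjustment or change score is stated.

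**The concern.** There are two separate problems.

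**Order.** The trial has a self-reported primary outcome, and no blinding is described; the taper date, which differs by arm, is written on the patient's prescription and discharge instructions. A baseline completed after allocation can therefore be coloured by knowledge of the arm. A BDI completed after allocation also cannot act as the pre-randomization screen that the exclusion criteria require.

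**Interval.** Allocation before surgery leaves the operation and then 48 hours before the first dose. In that time surgery may be cancelled, the patient may become unable to take part, or a seizure may occur. All such patients are already in the intent-to-treat set. Seizures before the first dose can count in the Fisher comparison although no treatment difference exists yet. The early allocation gains nothing in return: both arms take the same regimen until the one-week arm begins its taper at day 5.

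**Working it through.** **1. Can all the timing rules be met together?** Take each permitted time of allocation in turn.

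- *Before surgery, baseline also before surgery (as the Research Plan text allows).* Consent and the BDI can precede allocation. The Table of Events is not followed.
- *Before surgery, Table of Events followed.* Eligibility check, consent, BDI and Neurotoxicity Scale all come after allocation. This breaks the rules that consent and the BDI come first.
- *0-24 hours after surgery.* Only a preoperative baseline can precede allocation, so the table is again not followed.
- *24-48 hours after surgery.* All rules can be met, and the Abstract agrees.

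Only the last case is consistent with everything in the document. Even there, the Neurotoxicity Scale is nowhere tied to randomization; only consent and the BDI are.

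**2. What does the order affect?** The primary comparison uses the six-week score alone, so the baseline score does not enter it. Baseline does enter the BDI exclusion, the description of the arms, and any change from baseline in mood or neurotoxicity. Mood alteration is a secondary objective. A change analysis would also mix preoperative scores with scores taken one to two days after surgery.

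**3. What could undosed patients cost?** The plan gives 38 per group, 5.4 points and 80% power, but no SD, alpha, sidedness or dropout. The 38 therefore cannot be reproduced forwards. Solved backwards at two-sided 5% with the normal approximation:

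SD = 5.4 / [√(2/38) × (1.960 + 0.842)] = 5.4 / (0.2294 × 2.802) = 8.40.

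The t-test version gives 8.29. Across one- or two-sided 5%, Mann-Whitney efficiency of 1, 0.955 or 0.864, and 0 or 10% dropout, the implied SD runs from about 7.4 to 9.5.

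Let f be the share, equal in both arms, that is randomized but never dosed. The documents do not give f; 5% and 10% are assumptions.

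*(a) They have a six-week score but contribute no treatment contrast.* The difference becomes (1 − f) × 5.4, and power = Φ[(1 − f) × 2.802 − 1.960].

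- f = 5%: difference 5.13; Φ(2.662 − 1.960) = Φ(0.702) = 75.9%.
- f = 10%: difference 4.86; Φ(2.522 − 1.960) = Φ(0.562) = 71.3%.

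*(b) They have no six-week score.* The number per arm becomes 38 × (1 − f), and power = Φ[√(1 − f) × 2.802 − 1.960].

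- f = 5%: 36.1 per arm; Φ(2.731 − 1.960) = Φ(0.771) = 78.0%.
- f = 10%: 34.2 per arm; Φ(2.658 − 1.960) = Φ(0.698) = 75.8%.

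The SD cancels from both formulas once the design is taken to have 80% power, so its uncertainty does not alter these results. The choice of alpha and sidedness does.

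**The case against.** The best defence is that the table's column header is merely incomplete. The detailed text requires consent and the BDI before allocation, pairs the two scales at one baseline visit, and allows that visit before surgery. A site following the text would have both scales in hand before a preoperative allocation. The Abstract is summary wording, and the inclusion criterion is the operative rule.

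Much of this stands, and it limits the point. A reader might infer four stronger things that the documents do not support:

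- *That the plan makes some baselines follow allocation.* It does not prescribe this; it leaves it possible. But the Research Plan tells sites to work from the table, and the primary instrument has no stated order.
- *That the primary test is biased.* It is not, because no baseline value enters it.
- *That a seizure after randomization makes a patient ineligible.* The exclusion concerns known history at entry. A later seizure is a secondary outcome, and keeping that patient is what intent to treat means. The weakness is allocating early enough to bring in avoidable pre-dose events.
- *That the first-week seizure figure in the Background sizes the undosed share.* It is an upper figure for a whole week in mixed non-traumatic pathology, the protocol also cites a trial with few postoperative seizures, and a seizure does not by itself mean that no dose is taken.

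It is also fair to say that a patient whose surgery is cancelled has no score six weeks after surgery. Case (b) in the working is then closer than case (a). Finally, patients may go home before 48 hours, so a rule confining allocation strictly to 24-48 hours could lose some of them.

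**Conclusion.** The conflict is real. The permitted preoperative allocation cannot be reconciled with the Table of Events, and it disagrees with the Abstract. The consequence is a possible, not a planned, post-allocation baseline on an unblinded self-report scale. It bears on BDI-based eligibility, baseline description and any change analysis, and leaves the six-week primary comparison unbiased.

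The second consequence is avoidable loss of information: patients never operated on or dosed enter the intent-to-treat set, and pre-dose seizures add events that treatment cannot have influenced. The power loss is illustrative only. It rests on an assumed undosed share of 5-10%, equal in both arms, a two-sided 5% test, and a plan that truly has 80% power. On those terms power is about 76-71% if these patients are scored without contrast, or about 78-76% if they are missing.

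**What to change.** - Allow consent at any time, before or after surgery.
- Randomize only after surgery, as late as practical and no later than the 48-hour drug start, or before discharge if that comes first.
- Before allocation, re-confirm eligibility and have both the BDI and the Neurotoxicity Scale completed. Name the Neurotoxicity Scale explicitly, since at present only the BDI is tied to randomization.
- Bring the inclusion criterion, the baseline sentence in the Research Plan and the Table of Events into that one order. The table needs to separate consent, baseline scales, eligibility re-check and allocation instead of holding them in one column.
- Record whether each baseline was taken before or after surgery, so that any change analysis can take account of it.

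The cost is a few sentences and a revised table. Some consented patients will become screen failures instead of randomized patients, and staff must complete the scales and allocate before an early discharge so that the arm-specific prescription can be issued. Treatment itself is unaffected, because the arms do not diverge until the one-week taper.

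### The scheduled wean applies to every participant on a date fixed by arm, with no stated exception for someone who has had a seizure since entry

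*Combined protocol and SAP*

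**What the plan says.** The Research Plan sets one stopping rule for both arms: "All patients will be weaned off of the AED over 2 days". The start date depends only on the arm. "The taper is to commence at day 5 for the one week group", and in the six-week arm it begins two days before the stop date. The wean is arranged in advance: "The taper will be included on their prescription instructions" as well as on the discharge sheet, and a teach-back is used "to confirm they understand how to take and stop their medications when they go home".

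Four other places bear on the point.

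- **Entry.** The exclusion is "Known history of seizure activity". Participants must be "Able to be randomized prior to or up to 48 hours after surgery".
- **Drug start.** "Patients will begin study medication 48 hours post-op", whether or not they are still in hospital.
- **Guideline.** The Abstract reports a recommendation to discontinue "after the first post-operative week in patients without seizures".
- **Follow-up.** The Table of Events has two columns, baseline and six weeks, and diary data are collected or recorded at the second. Adverse events are collected at six weeks, or sooner if the patient makes contact.

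The section on possible discomforts or risks names seizures as something participants may suffer. It mentions seizure freedom only as a condition for keeping a patient off AEDs after a wean for intolerable side effects.

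**The concern.** The trial tests early withdrawal of a prophylactic drug in people with no known seizure history. A participant who has a seizure after entry no longer fits that description, yet the written rule still reduces and stops the drug on the scheduled day. The one-week arm carries over the guideline's timing but not its condition.

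The issue is patient safety. In the one-week arm the taper comes within days of surgery, is started by the patient from a pre-written sheet, and is preceded by no scheduled contact. The protocol writes a response for a raised BDI score (evaluation by the Principal Investigator, with possible actions listed). It writes none for a seizure, the event the drug is given to prevent.

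**Working it through.** **Step 1. Does any text hold the scheduled wean after a seizure?**

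| Text | What it covers | Does it hold the wean? |
|---|---|---|
| Exclusion for seizure history | Seizures known at entry | No; it cannot act on a later seizure |
| Seizure-free condition (risks section) | Withdrawal for intolerable side effects | No; it does not modify the scheduled wean |
| BDI of 14 or more (Research Plan) | Mood; may include stopping levetiracetam | No; unrelated to seizures |
| Adverse-event reporting (Research Plan) | New problems, if the patient makes contact | No; it opens a route but does not pause the taper |
| Diary and concomitant medications | Recording | No; diary data are collected at six weeks |

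**Step 2. How long is the interval that the entry exclusion cannot cover in the one-week arm?** The protocol does not say what day 5 is counted from. Drug starts 48 hours (2 days) after surgery. Days from surgery to the first reduced dose:

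- counted from surgery as day 0: 5
- counted from first dose as day 1: 2 + 4 = 6
- counted from first dose as day 0: 2 + 5 = 7

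Uncovered interval, by time of screening:

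- before surgery (possible, because randomization before surgery is allowed): 5 to 7 days
- at 24 hours: 5 − 1 to 7 − 1 = 4 to 6 days
- at 48 hours: 5 − 2 to 7 − 2 = 3 to 5 days

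The Table of Events places the eligibility check at 24 to 48 hours after surgery, so 3 to 6 days is the range under the tabulated schedule.

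**Step 3. How many participants might this affect?** The documents give no seizure rate for this population on levetiracetam. The risks p below are assumptions, applied to the 38 planned per arm. Expected number = 38p; chance of at least one = 1 − (1 − p)^38.

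| Assumed p | Expected of 38 | Chance of at least one |
|---|---|---|
| 1% | 0.38 | 32% |
| 5% | 1.9 | 86% |
| 10% | 3.8 | 98% |

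**Step 4. What would the fix cost the primary comparison?** The plan's figure is 38 per group for a 5.4-point difference at 80% power. It cannot be reproduced directly, because no SD, alpha or sidedness is stated. Assuming two-sided alpha 0.05 and a normal approximation for means (the planned test is Mann-Whitney), the SD it implies is

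SD = 5.4 × √38 / [√2 × (1.960 + 0.842)] = 8.40.

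Suppose, as a worst case, that a fraction f of the one-week arm stays on drug to week 6 and loses the whole benefit. The difference becomes 5.4 × (1 − f), and power = Φ(difference × √(38/2) / 8.40 − 1.960).

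- f = 1%: 5.4 × 0.99 = 5.35 points; Φ(0.81), about 79%
- f = 10%: 5.4 × 0.90 = 4.86 points; Φ(0.56), about 71%

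With one-sided alpha 0.05 the implied SD is 9.47, and f = 10% gives Φ(4.86 × √19 / 9.47 − 1.645) = Φ(0.59), about 72%. The choice of sidedness hardly matters here.

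**The case against.** The strongest reply is that the rule concerns prophylaxis. Once a patient has had a seizure, the drug is treatment and ordinary clinical care takes over. Nothing in the protocol forbids a physician from continuing or restarting levetiracetam, and the seizure-free condition for patients weaned for side effects suggests that the authors think the same way. A first seizure after craniotomy is also an obvious reason to call, some participants will still be in hospital, and an independent medical monitor reviews each adverse event.

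Much of this stands. A reader might infer that the protocol orders treatment to be withheld after a seizure; it does not. It is silent, and the silence sits beside an unconditional rule. Nor does the text support the inference that continued drug would go unseen. The diary collects seizures and daily medication intake, and REDCap captures concomitant medications. Only the decision, its reason and its date lack a field. It would also be wrong to conclude that patients are not told to call: the instruction sheets are not in the documents, and consent pages were removed before review.

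What does not stand is that these routes close the gap. Each depends on the patient making contact or on a clinician overriding a pre-printed instruction. None is required before the first reduced dose.

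On size, the Background's figure of up to 35% in the first week comes from a different craniotomy population, while a phenytoin trial cited there found a low overall incidence. Neither can be used as the rate for this trial.

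**Conclusion.** The point holds as a statement about the protocol text: the scheduled wean has no exception for a participant with a seizure after entry, and no contact or review precedes it. It is a patient-safety weakness that should be fixed, and a cheap one to fix. Confidence is high that the text is silent, and lower about the consequence, because clinicians would probably act and the patient-facing sheets cannot be seen.

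The number affected is unknown. The range in the working only shows what the assumed 1% to 10% risks imply.

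A reader might also infer that the rule biases the primary neurotoxicity comparison. The documents do not support that. The analysis is by intent to treat, and weaning everyone on schedule would, if anything, preserve the planned contrast. The loss of contrast in the working is a cost of the remedy, and much of it would arise anyway if clinicians continue the drug in ordinary care.

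**What to change.** Amend the Research Plan for both arms:

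1. Restrict the scheduled taper to participants who are seizure free since surgery.
2. After any post-operative seizure, hold the taper until the investigator or treating physician has reviewed the participant and decided. This requires a review; it does not mandate longer treatment.
3. Add one line to the existing prescription and discharge instructions, and to the teach-back: if you have had any seizure, call the study team before the first reduced dose.
4. Record the decision, its reason and its date in REDCap.
5. Keep the intent-to-treat analysis.

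The administrative cost is one conditional rule, one line on existing sheets, a small addition to the database and a few calls. Review and re-supply must be prompt. If only the scheduled tablets are dispensed (an assumption), the two taper days hold 2 × 1 = 2 tablets, which is one day at the full twice-daily dose. The statistical cost is some dilution of the contrast. At 1% staying on drug it is negligible. At the assumed worst case of 10% it is about 9 points of power (80% to about 71%), which should be accepted knowingly.

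### The six-week scoring window (post-op days 38 to 46) spans the long arm's taper and stop, so its primary scores can mix full-dose, half-dose and off-drug patients

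*Combined protocol and SAP*

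**What the plan says.** The Abstract sets the primary endpoint as "performance on a validated neurotoxicity scoring system at 6 weeks post-op". The Table of Events places the only post-baseline scoring at "6 weeks postop (+/- 4days", with a footnote on how it may be done: "May be completed during a routine office visit or by telephone".

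The Research Plan gives both arms 500 mg twice daily (1000 mg a day), for one week or for six. On the start it says "Patients will begin study medication 48 hours post-op". The taper, common to both arms, is described as "decreasing the dose to 500mg po every day for 2 days and then stop". Its timing is set separately by arm. In the short arm, "The taper is to commence at day 5 for the one week group". The long arm instead begins its half dose "at 2 days prior to the stop date for the 6 week group".

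The plan does not say whether the six weeks run from first dose or from surgery, or whether the stop date is the last dosing day or the first day without drug. Nothing ties scoring to the last full dose. On drug intake, the Research Plan says "Participants will maintain a diary that will collect seizure occurrences and daily medication intake", but no planned analysis uses the dose at the time of scoring.

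**The concern.** The hypothesis is that the one-week group has less neurotoxicity than patients on six weeks of levetiracetam. The contrast is clearest while the long arm is still taking the drug and the short arm is not. The course and the visit both end at about six weeks, but they are counted differently. The visit is dated from surgery with a nine-day window, while dosing starts two days after surgery and ends with a two-day half dose. Whether a long-arm patient is scored on full dose, on half dose or off drug then depends on when the visit or call happens to fall.

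If drug effects ease as the dose falls, long-arm patients scored late look more like the short arm and the primary difference shrinks. A null result could then mean that the longer course is no more neurotoxic, or that many long-arm patients were scored after the taper or stop. This matters because the trial is meant to inform clinical guidelines and there is no other post-baseline score to separate the two explanations.

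**Working it through.** **Inputs.** Start of drug: post-op day 2 (Research Plan). Taper: two days at 500 mg a day, half the full dose (Research Plan). Scoring: post-op day 42 ± 4, so days 38 to 46, nine days (Table of Events). Counting the first dose as dosing day 1, dosing day d is post-op day d + 1.

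**Calendar for the long arm.**

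| Reading | Taper (post-op days) | Off drug from | Full / half / off days in 38–46 | Half or off | Nominal day 42 |
|---|---|---|---|---|---|
| (a) Stop on dosing day 42, taper on dosing days 40–41, parallel to day 5 in the short arm | 41–42 | 43 | 3 / 2 / 4 | 6 of 9 (67%) | half dose |
| (b) 42 dosing days including the taper (dosing days 41–42) | 42–43 | 44 | 4 / 2 / 3 | 5 of 9 (56%) | half dose |
| (c) Six weeks counted from surgery, stop on post-op day 42 | 40–41 | 42 | 2 / 2 / 5 | 7 of 9 (78%) | off drug |
| (d) Taper added after 42 full-dose days | 44–45 | 46 | 6 / 2 / 1 | 3 of 9 (33%) | full dose |

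The text does not settle which reading is meant. Reading (a) follows the day-5 rule but gives 41 days of drug. Reading (b) gives the full 42. Reading (d) fits poorly with a taper that starts before the stop date. All three dose states occur in the window on each reading.

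**Short arm.** The latest possible stop is under (d): full dose on post-op days 2–8, taper on days 9–10, off from day 11. The short arm is therefore off drug throughout days 38–46.

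**The plan's own figure.** The plan states 38 per group for 5.4 points with 80% power. It gives no SD, alpha or sidedness, so the figure cannot be reproduced directly. Solving backwards with an assumed two-sided alpha of 0.05:

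SD = 5.4 / [√(2/38) × (1.960 + 0.842)] = 8.40

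Allowing for the Mann-Whitney test's efficiency of 0.955 under normality, SD = 8.40 × √0.955 = 8.21.

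**Illustration of dilution (not a finding).** Further assumptions: normal scores, SD 8.2, visits spread evenly over the nine days, 38 per arm. The mean difference is 5.4 × (full + h × half + o × off) / 9, where h and o are the shares of the effect remaining at half dose and off drug. Power is from simulated Mann-Whitney tests, 20,000 trials per case. With no dilution it is about 80%.

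| Reading | h = 0.5, o = 0: difference, power | h = 0.75, o = 0.5: difference, power |
|---|---|---|
| (a) | 5.4 × 4/9 = 2.4, about 23% | 5.4 × 6.5/9 = 3.9, about 51% |
| (b) | 5.4 × 5/9 = 3.0, about 33% | 5.4 × 7/9 = 4.2, about 56% |
| (c) | 5.4 × 3/9 = 1.8, about 14% | 5.4 × 6/9 = 3.6, about 45% |
| (d) | 5.4 × 7/9 = 4.2, about 56% | 5.4 × 8/9 = 4.8, about 68% |

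The column with o = 0 is an extreme, because it assumes that all effect is gone on the first day off drug. If h = o = 1, for instance because the scale looks back over weeks, nothing is lost.

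**A window before the taper.** The last full-dose day is post-op day 40 under (a), 41 under (b), 39 under (c) and 43 under (d). A five-day window on days 35–39 is full dose for the long arm and off drug for the short arm on all four.

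**The case against.** The strongest reply is that the trial compares assigned courses, not drug states. The Primary Objective speaks of a shorter and a longer course, the analysis is intent-to-treat, and the taper is part of each course. On that view a score at a fixed post-op time is what was intended, and nothing in the plan requires full dose at scoring. This partly stands: an on-drug score has to be chosen and written into the endpoint. It does not remove the problem. Intent-to-treat fixes who is analysed, not when they are measured, and under the present window the long arm's dose state is set by visit scheduling, which belongs to neither course.

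A second reply is that the harm is not shown. The recall period of the scale, the rate at which symptoms resolve and the spread of visit dates are not in the documents. This stands in full. A reader might infer from the illustration that the trial's true power is 14% to 56%. The documents do not support that, since those figures rest on stacked assumptions and the range runs up to no loss at all.

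A reader might also infer a bias that could produce a false positive. That does not follow: both arms share the window, and any dilution runs against the trial's own hypothesis.

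Visits clustering at day 42 would not help, because that day is full dose only under (d). The diary could show the dose on the day of scoring, but it cannot restore a score that was taken too late.

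**Conclusion.** The overlap is established by calendar arithmetic. On all four readings the long arm's taper and stop fall inside the scoring window, with 5 to 7 of 9 days at half dose or off drug if the taper is inside the course and 3 of 9 if it follows. Long-arm scores can therefore mix three dose states while the short arm is always off drug. The consequence is conditional: if symptoms ease with dose, sensitivity is lost and a null result is ambiguous. How much is lost is unknown. It would be wrong to conclude that most long-arm patients will be scored off drug, since the counts describe the days the plan allows and not where visits will fall. This is a cheap improvement to the timing of the primary endpoint, not a flaw that invalidates the comparison.

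**What to change.** 1. State which day is day 1, and list the taper and stop days for both arms.
2. In both arms, complete the Neurotoxicity Scale by office visit or telephone in one common window that closes before the long arm's taper. Post-op days 35–39 meet this on all four readings. If the schedule in step 1 differs from these, close the window on the long arm's last full-dose day. State in the endpoint definition that the score is taken at the end of full-dose treatment in the six-week arm.
3. State when the BDI is done: either with the scale or at the existing six-week contact, the same in both arms.
4. Keep diary and adverse-event collection at the six-week contact. Record the post-op day of scoring and the diary dose that day, for descriptive reporting only.

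The cost is a window of five days instead of nine, an earlier telephone contact for the many patients whose routine visit falls at six weeks, and possibly some missed scores. The last point deserves attention because the plan states no dropout allowance on the 38 per group. No extra patients or instruments are needed.
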